## 5.7 Interruption and termination of the study

If a grade 3 or higher adverse event occurs, radiation therapy will be paused and appropriate supportive care initiated. The study team will be informed immediately, and the principal investigator will be consulted regarding the possible continuation of radiation therapy.

Should a grade 4 toxicity occur during treatment within the study, irrespective of the planned interim analysis regarding adverse events, and which cannot be controlled with supportive measures, then the study intervention must be interrupted until the observed toxicity subsides. The toxicity must be documented as a serious adverse event (SAE). The principal investigator is entitled to terminate the clinical trial prematurely for relevant medical/administrative reasons if

- Serious, irreversible adverse events (toxicity grade 4 or 5) occur that are clearly related to the study intervention under investigation (i.e., radiation of the prostate and metastases).
- the targeted patient recruitment does not take place within a reasonable timeframe • the research question under investigation becomes obsolete during the study due to new scientific findings and no longer serves the scientific purpose  
should meet the standard
- serious data quality problems should occur that cannot be resolved  
can
- unforeseen circumstances arise at the individual center that prevent the continuation of the  
Do not allow clinical trial
- in the event of relevant and serious violations of the study protocol
- Compliance with legal or ethical regulations cannot be guaranteed  
can.

The reasons for discontinuing the study will be documented in detail. Patients still undergoing treatment at the time of discontinuation will receive a final examination, which will be documented in the eCRF. If a study physician raises ethical concerns regarding the continuation of the study, these concerns must be reported to the principal investigator immediately. The principal investigator, in consultation with the co-principals, will decide on the discontinuation of the study.

## 5.8 Patient Registration

Patients are registered after receiving information and giving their informed consent to participate in the study. Their data is then pseudonymized, and prospectively documented on standardized data collection forms (eCRF - REDCap). Once a patient has been enrolled in the study, they must provide feedback to the study center in Tübingen within 24 hours so that central registration can be completed.

# 6. Guidelines for radiotherapy

## 6.1 Specifications for systemic therapy (antihormonal therapy according to guidelines)

In accordance with the S3 guideline, the initiation of systemic antihormonal therapy is started six months prior to study screening by the treating urologists (either at a center or in private practice). This involves complete androgen blockade through a combination of ADT and NHT (e.g., apalutamide, enzalutamide, or others, as determined by the primary treating urologist). The choice of drug and NHT is determined by the tumor board or the primary treating urologist, in accordance with the S3 guideline. This is the standard therapy and not part of the study protocol presented here. When initiating long-term hormone therapy, each patient is offered radiation gynecomastia prophylaxis according to departmental standards. Systemic therapy should be initiated at least six months prior to study enrollment and the PSMA-PET/CT scan.

If the PSA level does not fall completely to  $<0.2$  ng/ml and thus the study inclusion criteria are met, systemic therapy will be continued until a significant PSA increase occurs (doubling of the baseline value or PSA doubling time of  $< 6$  months).

## 6.2 Guidelines for radiotherapy

The study involves irradiation using two irradiation schemes.  
planned (the applied scheme is recorded in the CRF):

- 1) Radiation therapy of the prostate
  - 5 x 7.25 Gy up to a total dose of 36.25 Gy (MRI-guided on the MR-Linac once daily, 2-3 days per week)
  - If the conditions for ultra-hypofractionated radiation therapy (MR-guided radiation therapy) are not guaranteed at the respective center, radiation therapy can be performed according to the respective departmental standard, e.g. analogous to the STAMPEDE study with e.g. 6 x 6.0 Gy or moderately hypofractionated analogous to the CHHiP protocol with 20 x 3.0 Gy up to a total dose of 60.0 Gy.

- 2) Radiation therapy for bone and lymph node metastases

- Analogous to department-internal standard, e.g. 3 x 9.0-10.0 Gy or 5 x 6.0-7.0 Gy at Lymph nodes (bulks) (once daily, 2-3 days per week)
- Alternatively, in cases of multiple lesions or large central venous extent, fractionation with, for example, [methods] is possible. 5 x 6.0 Gy, dosed to the 80% isodose, is recommended.
- If stereotactic radiotherapy of the metastases is not possible due to anatomical proximity to OARs, metastasis size, or proximity to any previous irradiations, moderately hypofractionated radiotherapy of the metastases can be performed according to an established standard of the respective center.

The decision regarding the fractionation scheme rests with the treating center and its established standard. SBRT (e.g., 3 x 9.0–10.0 Gy) should be preferred over moderate hypofractionation. Whether this is feasible is determined based on the anatomical location, the size of the metastases, any potential risk to the patient's status, and the expected normal tissue exposure. Stereotactic radiotherapy is only possible if the limits for organs at risk are not exceeded (see Section 6.3 Treatment Planning).

The radiation therapy should be administered as IMRT with daily IGRT.

## 6.3 Radiation therapy planning

### 6.3.1 Planning CT

Radiation therapy planning is performed using a planning CT scan, which is carried out in a reproducible patient position. For this purpose, moderate bladder filling and a rectum that is as empty as possible should be ensured for prostate radiation planning. The scan area for prostate radiation should extend caudally to the lesser tubercle and encompass the entire pelvis up to the cranial border of L2/3.

Depending on clinical necessity, individual aids can be adapted – particularly for planning the radiation therapy of metastases (vacuum mattress, abdominal belt, respiratory gating, custom mask). The slice thickness should be 1 mm for planning prostate radiation therapy and 1–2 mm for radiation therapy of metastases. For prostate radiation therapy, depending on the established workflow at the respective center, MRI-guided treatment planning can also be performed.

### 6.3.2 Treatment planning

All radiation treatment plans applied within the study and the PSMA-PET/CT or PSMA-PET/MRI images used for treatment planning are transmitted and stored electronically in pseudonymized form in the database at the study center. The evaluation of the PSMA-PET/CT scans according to RECIP criteria or PROMISE V2 is performed centrally by the Department of Nuclear Medicine Tübingen.

### 6.3.3 Planning prerequisites

For radiation therapy planning, pre-therapeutic diagnostics should be rigorously documented. If possible, the PSMA-PET data should be loaded into the radiation therapy planning system. Radiation therapy planning is performed using the planning system established at the respective location. For target volumes that move with respiration, radiation therapy planning is based on a 4D CT scan or a CT scan with respiratory gating, according to the respective center's established standard.

### 6.3.4 Documentation of irradiation parameters

The documentation of the irradiation parameters is done in the eCRF using REDCap.

### 6.4 Organs at Risk In

principle, all organs that are clearly distinguishable and located in anatomical relation to the target volume (distance to the PTV border <5 cm) should be contoured as organs at risk (OARs).

#### 6.4.1 Pelvic organs at risk during prostate irradiation

The following OARs should be contoured for planning prostate radiation therapy:

OAR	CT/MRI	definition
bubble	CT/MRI	Bladder in CT scan (including outer wall)
rectum	CT/MRI	Analog RTOG (starting from the lowest level of the ischial tuberosity, cranial end in the region of the rectosigmoid junction, penile bulb (part of the
Bulbus	CT/MRI (T2w)	spongiosum bulb) under the urogenital diaphragm [29] best visualized in mpMRI (T2w)
right femoral head	CT	Right femoral head
left femoral head	CT	Left femoral head
pubis	CT	symphysis and pubic bone
Colon	CT	Contour the colon, provided the colon is 2cm above the The highest axial PTV layer is included
Small intestine	CT scan, possibly with MRI	Contour the small intestine if the small intestine is contained 2 cm above the highest axial PTV layer.
urethra	MRI (T2w)	Prostatic urethra from the upper surface of the urethra bulb to the junction with the prostate gland and its opening into the bladder (in mpMRI)

\* in anatomical positional relationships

#### 6.4.2 Organs at risk during radiotherapy for metastases

The following organs, considered at risk for planning metastasis radiation therapy, should be contoured using CT scans based on their anatomical relationship (as shown):

- Entire bone affected by metastasis; adjacent bones • In the case of vertebral body metastases: Separately, vertebral body and vertebral arch
- Brain
- Cerebellum
- Pituitary gland
- Right and left eye
- Right and left lacrimal glands
- right and left optic nerve
- Chiasma
- right and left inner ear

- Brainstem
- Spinal cord
- Brachial plexus and sacral plexus
- Thyroid gland
- Trachea
- Right and left lungs
- Right and left main bronchus
- Aorta, vena cava, pulmonary artery and vein
- Heart
- Esophagus
- Stomach
- Duodenum
- Liver (entire body) •
- Colon
- Pancreas
- Right and left kidney
- Right and left ureter
- Rectum
- Bladder
- Left and right femoral head

## 6.5 Image-guided radiotherapy

Since SBRT is being performed, daily imaging should be carried out before each fraction delivery, using the best available image guidance (ideally cone-beam CT). For prostate irradiation, daily image guidance is performed using cone-beam CT or MRI.

Deviations from the isocenter greater than 0.5 mm are corrected by repositioning the treatment table.

## 6.6 Target volume definition

### 6.6.1 Target volume definition for ultrahypofractionated prostate irradiation:

The target volume definition for ultrahypofractionated radiotherapy of the prostate is analogous to the PACE-B study, taking into account the current recommendation of ESTRO-ACROP [30].

#### *Clinical target volume (CTV)*

CTV_3625	Prostate + any extracapsular tumor
CTV_3000*	CTV_3625 plus seminal vesicles

\* if T3b or T4 stage with seminal vesicle involvement

#### *Planning target volume (PTV)*

PTV_3625	CTV_3625 + 3 mm all around
PTV_3000	(CTV_3625 + CTV_3000) + 3 mm on all sides

### 6.6.2 Target volume definition for moderately hypofractionated radiotherapy of the prostate:

The target volume definition for moderately hypofractionated radiotherapy of the prostate is analogous to the CHHiP trial, taking into account the current ESTRO-ACROP recommendation [27, 30]. If radiotherapy is chosen according to the respective departmental standard (e.g., analogous to the STAMPEDE study), the prescriptions and dose constraints of the respective department apply.

#### *Clinical target volume (CTV)*

CTV_6000	Prostate + any extracapsular tumor
CTV_5700+SB*	CTV_6000 + SB

\* if T3b or T4 stage with seminal vesicle involvement

#### *Planning target volume (PTV)*

PTV_6000	CTV_6000 + 6 mm/5 mm dorsal (rectum)
PTV_5700+SB*	(CTV_6000 + SB) + 6mm/5 mm dorsally (rectum)

In the RIALTO study – unlike the CHHiP trial, which used 3D conformal radiation therapy with three weekly position checks based on the bony structures of the pelvis – IGRT with daily verification (CBCT with prostate position check) and the prescription of normal tissue constraints as part of IMRT. Therefore, bowel distension staging analogous to CHHiP is not required for radiation therapy in the present study, as the settings are verified daily and adjusted based on IGRT position.

### 6.6.3 Target volume definition for stereotactic radiotherapy of metastases:

Pre-therapeutic imaging (at least CT of the PSMA-PET/CT, and if possible also PET) should be fused with the planning CT for target volume definition. Target volume definition is performed according to the recommendations of ICRU Report 62 [31], the ESTRO guideline for stereotactic radiotherapy of spinal metastases [32], the consensus guidelines for postoperative radiotherapy of spinal metastases, and the recommendations for target volume definition for stereotactic radiotherapy of non-spinal bone metastases [33]. Metastases requiring postoperative radiotherapy or those stabilized with metal will be treated outside the study protocol according to departmental standard.

GTV_X*	Extent of metastasis on CT scan (+/- PET)
CTV_X*	GTV + 2 mm all around; adaptation to anatomical boundaries
PTV_X*	CTV + 3 mm all around to compensate for movement and intra-/interfractional positioning uncertainty; if necessary, adaptation of the margin according to proximity to risk structures or possibility of intrafractional position control (center-specific)

\*Name the target volume according to its anatomical location, e.g., 5th rib\_right

### 6.6.4 Target volume definition for moderately hypofractionated/normofractionated metastasis radiotherapy

If stereotactic radiotherapy is not possible due to the size of the tumor or its anatomical proximity to risk structures, moderately hypofractionated or normofractionated radiotherapy can be performed according to departmental standards. Pre-therapeutic imaging (at least CT or PSMA-PET/CT, 28

If possible, PET should be fused with the planning CT scan for target volume definition. Target volume definition is performed according to the recommendations of ICRU Report 62 [31]. A BED of 100 Gy should be achieved if possible. Deviations should be documented in the CRF.

GTV_X*	Extent of metastasis on CT scan (+/- PET)
CTV_X*	GTV + 3 mm all around; adaptation to anatomical boundaries
PTV_X*	CTV + 3-7 mm all around (depending on departmental standard and method of position control) to compensate for movement and intra-/interfractional storage uncertainty; margin adjustment if necessary. proximity to risk structures

## 6.7 Dosage prescription and dose limits

### 6.7.1 Dosage Prescription

Target volume	Dose prescription
Prostate UHF	PTV_3625: 36.25 Gy in 7 Gy per fraction; D98% (PTV_3625) $\ddot{y}$ 33.25 Gy, D99% (CTV_3625) $\ddot{y}$ 34.5 Gy; D50% $\ddot{y}$ 35 Gy PTV_3000: 30 Gy in 6 Gy per fraction; D98% (PTV_3000) $\ddot{y}$ 28.5 Gy; D99% (CTV_3000) $\ddot{y}$ 28.5 Gy; D50% $\ddot{y}$ 30 Gy
Prostate MHF	PTV_6000: 60 Gy in 3 Gy per fraction; D99% (PTV_6000) $\ddot{y}$ 5 Gy, D98% (CTV_6000) $\ddot{y}$ 57 Gy; D1% $\ddot{y}$ 63 Gy; D50 = 60 Gy + 1% PTV_5700: 57 Gy in 2.85 Gy per fraction; D98% (PTV_5700) $\ddot{y}$ 51.3 Gy, D98% (CTV_5700) $\ddot{y}$ 54.15 Gy
Metastases SBRT	PTV min. 80% of the prescribed dose. GTV recorded at min. 95% of the prescribed dose; the maximum should be 120%. The prescribed dose should not be exceeded.
Metastases NF or MHF PTV D98%	90% of the prescribed dose, D2% <107%, CTV D98% - 95% of the prescribed dose, D2% < 110%. Global maximum <115%.

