If MR-guided ultra-hypofractionated radiotherapy of the prostate is not possible, moderately hypofractionated radiotherapy with 20 x 3.0 Gy fractions or according to departmental standards (e.g., 6 x 6.0 Gy analogous to the STAMPEDE trial) can be performed. Due to the lower fractional dose, this is administered as CT-guided IGRT with daily cone-beam CT monitoring and a treatment duration of 10–20 minutes. The radiotherapy is administered daily on weekdays, corresponding to a total treatment duration of four weeks.

The treatment planning for metastases is carried out analogously (CT-guided radiation therapy; MRI-guided radiation therapy is also possible for lymph node metastases); two appointments are scheduled for patient education and treatment planning. If possible, metastases should be treated stereotactically with 3-5 treatment sessions. There are no dose or fractionation guidelines; the prescription for metastases is based on the department's internal standard. If stereotactic radiation therapy is not possible due to normal tissue tolerance, normofractionation is performed.

**Specific side effects of radiation therapy:** In preparation for each radiation fraction, it is important to adhere to a fluid intake protocol with a target bladder volume of 200-250 mL for the radiation treatment. If the rectal ampulla is very full, an enema should be administered. During the MRI examination (for radiation planning/radiation), in rare cases, overheating, ringing in the ears, and tinnitus may occur. In very rare cases, hearing damage may occur if hearing protection is not fitted correctly, or headaches may develop.

Patients with a pacemaker or other contraindications to an MRI examination should not undergo an MRI scan.

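### Section 6.7.1, as available, sets the PTV_6000 D99% criterion at 5 Gy on a 60 Gy prescription: check the source cell and, unless a digit was lost, replace it with an explicit minimum

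*Protocol*

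**What the plan says.** In the Prostate MHF row of Protocol section 6.7.1, PTV_6000 is prescribed 60 Gy in 3 Gy fractions with "D99% (PTV_6000) $\ddot{y}$ 5 Gy, D98% (CTV_6000) $\ddot{y}$ 57 Gy". The same cell gives a D1% of 63 Gy and a D50 of 60 Gy. The companion volume, used when the seminal vesicles are involved, reads "PTV_5700: 57 Gy in 2.85 Gy per fraction; D98% (PTV_5700) $\ddot{y}$ 51.3 Gy".

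The ultrahypofractionated row above has the same structure. Its D99% entries, both for CTVs, are "D99% (CTV_3625) $\ddot{y}$ 34.5 Gy; D50% $\ddot{y}$ 35 Gy" and "D99% (CTV_3000) $\ddot{y}$ 28.5 Gy". It also states "PTV_3625: 36.25 Gy in 7 Gy per fraction", whereas section 6.2 has "5 x 7.25 Gy up to a total dose of 36.25 Gy".

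Section 4.3.2 makes clear that 20 x 3.0 Gy is the alternative schedule: "If MR-guided ultra-hypofractionated radiotherapy of the prostate is not possible, moderately hypofractionated radiotherapy with 20 x 3.0 Gy fractions". Section 6.7.3 says that the dose prescription and normal tissue constraints for this schedule come from the CHHiP trial and cites the source. No other section gives a coverage value for PTV_6000.

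**The concern.** D99% is the dose that 99% of a volume receives or exceeds, so for a planning target volume it serves as a near-minimum. A value of 5 Gy on a 60 Gy plan cannot do that job.

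What is at stake is the margin around the prostate, 6 mm and 5 mm towards the rectum (6.6.2). Section 6.7.3 limits the rectal volume at 57 and 60 Gy, which pulls a plan towards giving up coverage on the rectal side. A PTV minimum is the usual counterweight. If the source reads 5 Gy, the table sets no effective counterweight for patients treated to PTV_6000 alone. A poorly covered margin would then not count as a departure from the stated criterion.

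**Working it through.** **Step 1. Express each coverage value as a share of its own prescription.** All inputs are from the table in 6.7.1. The D50% and D1% entries are left out because they are median and maximum doses.

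| Volume and metric | Value (Gy) | Prescription (Gy) | Share |
|---|---|---|---|
| PTV_3625 D98% | 33.25 | 36.25 | 91.7% |
| CTV_3625 D99% | 34.5 | 36.25 | 95.2% |
| PTV_3000 D98% | 28.5 | 30 | 95.0% |
| CTV_3000 D99% | 28.5 | 30 | 95.0% |
| **PTV_6000 D99%** | **5** | **60** | **8.3%** |
| CTV_6000 D98% | 57 | 60 | 95.0% |
| PTV_5700 D98% | 51.3 | 57 | 90.0% |
| CTV_5700 D98% | 54.15 | 57 | 95.0% |

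No share that the table uses elsewhere gives 5 Gy from 60 Gy.

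**Step 2. Try both directions of the lost sign.** As a minimum, 5 Gy is met by any realistic 60 Gy plan. As a maximum, it would require at least 1% of the PTV to receive no more than 5 Gy. A cold spot of that size in the margin could coexist numerically with CTV_6000 D98% 57 Gy and D50 = 60 Gy, but it defeats the prescription that those two criteria express. Neither reading is usable.

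**Step 3. See what the table's pattern suggests.**
- Range: 0.90 x 60 = 54 Gy to 0.95 x 60 = 57 Gy. The PTV_3625 share gives 0.917 x 60 = 55 Gy.
- The only PTV and CTV pair with the same metric is on the same schedule: 51.3 / 54.15 = 0.947. Applied to CTV_6000, 0.947 x 57 = 54.0 Gy, as a D98%.

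This is an assumption. The three PTV comparators are all D98%, and the disputed entry is a D99%. D99% cannot exceed D98% in the same volume, so the same figure set as a D99% would be the stricter criterion.

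**Step 4. Find what still protects the margin.** With seminal vesicle involvement, PTV_5700+SB is built from CTV_6000 plus the seminal vesicles with the same margins (6.6.2). Its D98% of 51.3 Gy is 51.3 / 60 = 85.5% of 60 Gy and covers the same margin. Without involvement, no PTV floor remains.

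**Step 5. Check the second entry.** 5 x 7 = 35 Gy, against 5 x 7.25 = 36.25 Gy in 6.2 and in the same cell's own total. Two limits in that cell would also fit 35 Gy (33.25 / 35 = 0.95, and the D50% of 35 Gy), so they are worth a look when the fraction dose is corrected.

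**The case against.** The strongest objection is that this is damage from reading the PDF. The comparison signs in the table are corrupted, including the one directly before the 5. The last row has a metric moved into its label, and the table in 6.7.3 shows similar damage. A lost second digit from 54, 55 or 57 would give exactly this entry. The 7 Gy could be a truncated 7.25 and so does not place the slip in the source.

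This stands in part: the document cannot prove what the source prints. It does not dispose of the point. The visible damage replaces signs consistently. Of the eleven numerals that follow a garbled sign, ten fit their prescriptions: the seven shares in the table above, the D50% values (35 / 36.25 = 96.6%, 30 / 30 = 100%) and the D1% (63 / 60 = 105%). Decimals such as 33.25 and 54.15 survive. Running text also has a dose slip: section 4.3.2 gives 5 x 7.5 Gy and later 7.25 Gy for the same treatment.

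A second objection is that the comparison mixes PTV with CTV and D98% with D99%. That is fair. It limits how precisely a replacement can be inferred, but it does not make 8.3% plausible.

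A third is that safeguards exist, and they do. CTV_6000 D98% and D50 would catch gross underdosage. Centres on a departmental standard use their own constraints (6.6.2). Section 6.7.3 names the constraint source, and section 10.2 sends ambiguities to the study center.

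**Conclusion.** The point holds as a minor dose-table error, conditional on the source cell. As available, the PTV_6000 D99% entry is 8.3% of prescription, against 90.0% to 95.2% for the other seven prostate coverage values, and it works neither as a minimum nor as a maximum. It is a wrong or incomplete entry and not a calculation that went astray, since nothing in the protocol computes 5 Gy.

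The effect is confined to PTV-margin coverage in patients on the fallback 20 x 3.0 Gy schedule without seminal vesicle involvement. The protocol does not say how many patients that will be. The endpoint, the sample size of 27 and the primary test are untouched.

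A reader might infer that the plan accepts underdosing of the prostate to 5 Gy, or that the sponsor's document certainly contains this figure. The documents support neither. CTV_6000 D98% 57 Gy and D50 = 60 Gy stand in the same cell, and a lost digit cannot be excluded. Nor do they establish 54 Gy as the intended value; that is an analogy with PTV_5700.

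**What to change.** Check the cell in the sponsor's source. Unless it shows a lost digit, replace 5 Gy with the PTV_6000 minimum from the constraint source cited in 6.7.3. Write it with an explicit at-least sign and name the metric (D98% or D99%). Expect a value of about 54 to 57 Gy, but take the figure from the source and not from this range.

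In the same table, correct 7 Gy per fraction to 7.25 Gy to match 6.2, and confirm that the limits beside it refer to 36.25 Gy.

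The cost is two table entries. If any 20 x 3.0 Gy plans have already been applied, they can be checked against the corrected value from the central store, because 6.3.2 has all applied plans sent to the study center.
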